	protocol for defining the CTC grade/severity)		reduced cardiac function. Consider discussing with the study physician, as needed. Monitor subjects for signs and symptoms of myocarditis (new onset or worsening chest pain, arrhythmia, shortness of breath, peripheral edema). As some symptoms can overlap with lung toxicities, simultaneously evaluate for and rule out pulmonary toxicity as well as other causes (e.g., pulmonary embolism, congestive heart failure, malignant pericardial effusion). Consult a Cardiologist early, to promptly assess whether and when to complete a cardiac biopsy, including any other diagnostic procedures. Initial work-up should include clinical evaluation, BNP, cardiac enzymes, ECG, echocardiogram (ECHO), monitoring of oxygenation via pulse oximetry (resting and exertion), and additional laboratory work-up as indicated. Spiral CT or cardiac MRI can complement ECHO to assess wall motion abnormalities when needed. Patients should be thoroughly evaluated to rule	
			out any alternative etiology (e.g., disease progression, other medications, or infections).	
	Grade 1	No dose modifications required unless clinical suspicion is high, in which case hold study drug/study regimen dose during diagnostic work-up for other etiologies. If	For Grade 1: • Monitor and closely follow up in 2 to 4 days for clinical symptoms, BNP, cardiac enzymes, ECG,	

	Immune-mediated Reactions			
		study drug/study regimen is held, resume after complete resolution to Grade 0.	 ECHO, pulse oximetry (resting and exertion), and laboratory work-up as clinically indicated. Consider using steroids if clinical suspicion is high. 	
	Grade 2, 3, or 4	If Grade 2 Hold study drug/study regimen dose until resolution to Grade 0. If toxicity rapidly improves to Grade 0, then the decision to reinitiate study drug/study regimen will be based upon treating physician's clinical judgment and after completion of steroid taper. If toxicity does not rapidly improve, permanently. discontinue study drug/study regimen. If Grade 3-4, permanently discontinue study drug/study regimen.	For Grade 2-4: - Monitor symptoms daily, hospitalize. - Promptly start IV methylprednisolone 2 to 4 mg/kg/day or equivalent after Cardiology consultation has determined whether and when to complete diagnostic procedures including a cardiac biopsy. - Supportive care (e.g., oxygen). - If no improvement within 2 to 3 days despite IV methylprednisolone at 2 to 4 mg/kg/day, promptly start immunosuppressive therapy such as TNF inhibitors (e.g., infliximab at 5 mg/kg IV, may be repeated at 2 and 6 weeks after initial dose at the discretion of the treating provider). Caution: It is important to rule out sepsis and refer to infliximab label for general guidance before using infliximab. Infliximab is contraindicated for patients who have heart failure.	
Myositis/Polymyositis	Any Grade	General Guidance	For Any Grade:	
	(Refer to NCI CTCAE applicable version in study protocol for defining the CTC grade/severity)		 Monitor patients for signs and symptoms of poly/myositis. Typically, muscle weakness/pain occurs in proximal muscles including upper arms, thighs, shoulders, hips, neck and back, but rarely affects the extremities including hands and fingers; also difficulty breathing and/or trouble swallowing can occur and progress rapidly. 	

Immune-mediated Rea	ections
	Increased general feelings of tiredness and fatigue may occur, and there can be newonset falling, difficulty getting up from a fall, and trouble climbing stairs, standing up from a seated position, and/or reaching up. — If poly/myositis is suspected, a Neurology consultation should be obtained early, with prompt guidance on diagnostic procedures. Myocarditis may co-occur with poly/myositis; refer to guidance under Myocarditis. Given breathing complications, refer to guidance under Pneumonitis/ILD. Given possibility of an existent (but previously unknown) autoimmune disorder, consider Rheumatology consultation. — Consider, as necessary, discussing with the study physician. — Initial work-up should include clinical evaluation, creatine kinase, aldolase, LDH, BUN/creatinine, erythrocyte sedimentation rate or C-reactive protein level, urine myoglobin, and additional laboratory work-up as indicated, including a number of possible rheumatological/antibody tests (i.e., consider whether a rheumatologist consultation is indicated and could guide need for rheumatoid factor, antinuclear antibody, anti-smooth muscle, antisynthetase [such as anti-Jo-1], and/or signal-recognition particle antibodies). Confirmatory testing may include electromyography, nerve conduction studies, MRI of the muscles, and/or a muscle biopsy. Consider Barium

Immune-mediated Reactions			
		swallow for evaluation of dysphagia or dysphonia. - Patients should be thoroughly evaluated to rule out any alternative etiology (e.g., disease progression, other medications, or infections).	
Grade 1	No dose modifications.	For Grade 1: - Monitor and closely follow up in 2 to 4 days for clinical symptoms and initiate evaluation as clinically indicated. - Consider Neurology consult. - Consider, as necessary, discussing with the study physician.	
Grade 2	Hold study drug/study regimen dose until resolution to Grade ≤1. Permanently discontinue study drug/study regimen if it does not resolve to Grade ≤1 within 30 days or if there are signs of respiratory insufficiency.	For Grade 2: - Monitor symptoms daily and consider hospitalization. - Obtain Neurology consult, and initiate evaluation. - Consider, as necessary, discussing with the study physician. - If clinical course is rapidly progressive (particularly if difficulty breathing and/or trouble swallowing), promptly start IV methylprednisolone 2 to 4 mg/kg/day systemic steroids along with receiving input from Neurology consultant - If clinical course is not rapidly progressive, start systemic steroids (e.g., prednisone 1 to 2 mg/kg/day PO or IV equivalent); if no improvement within 2 to 3 days, continue additional work up and start treatment with	

Immune-mediated Reactions			
		IV methylprednisolone 2 to 4 mg/kg/day If after start of IV methylprednisolone at 2 to 4 mg/kg/day there is no improvement within 2 to 3 days, consider starting another immunosuppressive therapy such as TNF inhibitors (e.g., infliximab at 5 mg/kg IV, may be repeated at 2 and 6 weeks after initial dose at the discretion of the treating provider). Caution: It is important to rule out sepsis and refer to infliximab label for general guidance before using infliximab.	
Grade 3 or 4	For Grade 3: Hold study drug/study regimen dose until resolution to Grade ≤1. Permanently discontinue study drug/study regimen if Grade 3 imAE does not resolve to Grade ≤1 within 30 days or if there are signs of respiratory insufficiency. For Grade 4: Permanently discontinue study drug/study regimen.	For Grade 3 or 4 - Monitor symptoms closely; recommend hospitalization. - Obtain Neurology consult. - Consider discussing with the study physician, as needed. - Promptly start IV methylprednisolone 2 to 4 mg/kg/day systemic steroids along with receiving input from Neurology consultant. - If after start of IV methylprednisolone at 2 to 4 mg/kg/day there is no improvement within 2 to 3 days, consider starting another immunosuppressive therapy such as TNF inhibitors (e.g., infliximab at 5 mg/kg IV, may be repeated at 2 and 6 weeks after initial dose at the discretion of the treating provider). Caution: It is important to rule out sepsis and refer to infliximab label for general guidance before using infliximab. - Consider whether patient may require IV IG, plasmapheresis.	

AChE = acetylcholine esterase; ACTH = adrenocorticotropic hormone; ADL = activities of daily living; AE = adverse event; ALP = alkaline phosphatase; ALT = alanine aminotransferase; ASCO = American Society of Clinical Oncology; AST = aspartate aminotransferase; BNP = brain natriuretic peptide; BUN = blood urea nitrogen; CT = computed tomography; CTCAE = Common Terminology Criteria for Adverse Events; ECG = electrocardiogram; FDA = Food and Drug Administration, GI = gastrointestinal; HgA1c = hemoglobin A1c; IG = immunoglobulin; ILD = interstitial lung disease; imAE = immune-mediated adverse event; IV = intravenous; LDH = lactate dehydrogenase; LFT = liver function test; LLN = lower limit of normal; MRI = magnetic resonance imaging; NCI = National Cancer Institute; NCCN = National Comprehensive Cancer Network; PJP = *Pneumocystis jirovecii* pneumonia (formerly known as *Pneumocystis carinii* pneumonia); PO = by mouth; T₃ = triiodothyronine; T₄ = thyroxine; TB = total bilirubin; TNF = tumor necrosis factor; TSH = thyroid stimulating hormone; ULN = upper limit of normal.

- ^a ASCO Educational Book 2015 "Managing Immune Checkpoint Blocking Antibody Side Effects" by Michael Postow MD.
- ^b FDA Liver Guidance Document 2009 Guidance for Industry: Drug Induced Liver Injury Premarketing Clinical Evaluation.
- ^c NCCN Clinical Practice Guidelines in Oncology "Management of Immunotherapy-Related Toxicities" Version 1.2020 December 2019

Appendix E-2: Durvalumab Treatment Modification and Toxicity Management Guidelines for Infusion-related Reactions

	Infusion-R	elated Reactions
Severity Grade of the Event (Refer to NCI CTCAE applicable version in study protocol for defining the CTC grade/severity)	Dose Modifications	Toxicity Management
Any Grade	General Guidance	For Any Grade: - Management per institutional standard at the discretion of investigator - Monitor subjects for signs and symptoms of infusion-related reactions (e.g., fever and/or shaking chills, flushing and/or itching, alterations in heart rate and blood pressure, dyspnea or chest discomfort, skin rashes etc.) and anaphylaxis (e.g., generalized urticaria, angioedema, wheezing, hypotension, tachycardia)
Grade 1 or 2	The infusion rate of study drug/study regimen may be decreased by 50% or temporarily interrupted until resolution of the event The infusion rate of study drug/study regimen may be decreased 50% or temporarily interrupted until resolution of the event Subsequent infusions may be given at 50% of the initial infusion rate	 For Grade 1 or Grade 2: Acetaminophen and/or antihistamines may be administered per institutional standard at the discretion of the investigator Consider premedication per institutional standard prior to subsequent doses Steroids should not be used for routine premedication of ≤Grade 2 infusion reactions
Grade 3/4	Permanently discontinue study drug/study regimen	For Grade 3 or 4: Manage severe infusion-related reactions per institutional standards (e.g., IM epinephrine, followed by IV diphenhydramine and famotidine, and IV glucocorticoid)

CTCAE = Common Terminology Criteria for Adverse Events; IM = Intramuscular; IV = Intravenous; NCI = National Cancer Institute.

Appendix E-3: Durvalumab Treatment Modification and Toxicity Management Guidelines for Non-Immune-Mediated Reactions

Non-immune Mediated Reactions (Note: As applicable, for early phase studies, the following sentence may be added: "Any event greater than or equal to Grade 2, please discuss with Study Physician" CTC **Dose Modification Toxicity Management Grade/Severity Grade of the Event** (Refer to NCI CTCAE applicable version in study protocol for defining the CTC grade/severity) Note: dose modifications are not required for adverse events not deemed to be related to Treat accordingly as per institutional **Any Grade** study treatment (i.e., events due to underlying disease) or for laboratory abnormalities not standard deemed to be clinically significant. Grade 1 No dose adjustment Treat accordingly as per institutional standard Treat accordingly as per institutional Grade 2 Hold study drug/study regimen until resolution to \leq Grade 1 or baseline standard Grade 3 Hold study drug/study regimen until resolution to \leq Grade 1 or baseline Treat accordingly as per institutional standard For AEs that downgrade to < Grade 2 within 7 days or resolve to < Grade 1 or baseline within 14 days, resume study drug/study regimen administration. Otherwise, discontinue study drug/study regimen Discontinue Study drug/study regimen (Note: for Grade 4 labs, decision to discontinue Grade 4 Treat accordingly as per institutional would be based on accompanying clinical signs/symptoms and as per Investigator's standard clinical judgment and in consultation with the sponsor.)

AChE = acetylcholine esterase; ADA = American Dietetic Association; AE = adverse event; ALP = alkaline phosphatase; ALT = alanine aminotransferase; AST = aspartate aminotransferase; CT = computed tomography; GI = gastrointestinal; IDS=Infectious Disease Service; ILD = interstitial lung disease; IM = intramuscular; imAE = immune-mediated adverse event; IV = intravenous; NCI CTCAE = National Cancer Institute Common Terminology Criteria for Adverse Events; PO = by mouth; TNF = tumor necrosis factor; TSH = thyroid stimulating hormone; ULN = upper limit of normal.

Note: As applicable, for early phase studies, the following sentence may be added: "Any event greater than or equal to Grade 2, please discuss with Study Physician."

Appendix E-4: Durvalumab Treatment Modification and Toxicity Management Guidelines for Other—immune-mediated Reactions

	Other-immune-mediated Reactions				
Severity Grade of the Event (Refer to NCI CTCAE applicable version in study protocol for defining the CTC grade/severity)	Dose Modification	Toxicity Management			
Any Grade	Note: It is possible that events with an inflammatory or immune mediated mechanism could occur in nearly all organs, some of them are not noted specifically in these guidelines (e.g. immune thrombocytopenia, haemolytic anaemia, uveitis, vasculitis).	 The study physician may be contacted for immune-mediated reactions not listed in the "specific immune-mediated reactions" section Thorough evaluation to rule out any alternative etiology (e.g., disease progression, concomitant medications, and infections) Consultation with relevant specialist Treat accordingly, as per institutional standard. 			
Grade 1	No dose adjustment	Monitor as clinically indicated			
Grade 2	 Hold study drug/study regimen until resolution to ≤Grade 1 or baseline. If toxicity worsens, then treat as Grade 3 or Grade 4. Study drug/study regimen can be resumed once event stabilizes to Grade ≤1 after completion of steroid taper. Consider whether study drug/study regimen should be permanently discontinued in Grade 2 events with high likelihood for morbidity and/or mortality when they do not rapidly improve to Grade <1 upon treatment with systemic steroids and following full taper 	For Grade 2, 3, or 4 Treat accordingly, as per institutional standard, appropriate clinical practice guidelines, and other society guidelines (e.g., NCCN, ESMO)			

Other-immune-mediated Reactions			
Severity Grade of the Event (Refer to NCI CTCAE applicable version in study protocol for defining the CTC grade/severity)	Dose Modification	Toxicity Management	
Grade 3	Hold study drug/study regimen		
Grade 4	Permanently discontinue study drug/study regimen		

AE Adverse event; CTCAE Common Terminology Criteria for Adverse Events; NCI National Cancer Institute.

Note: As applicable, for early phase studies, the following sentence may be added: "Any event greater than or equal to Grade 2, please discuss with Study Physician."

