7.2.4. Dose Modifications and Interruptions

Subjects will be evaluated for AEs at each visit with the NCI CTCAE Version 4.03 or higher as a guide for the grading of severity.

If the treatment has been interrupted and the next cycle is delayed beyond Day 28 of the prior cycle, then Day 1 of the next cycle will be defined as the first day that study treatment is resumed.

- If DURVA is permanently discontinued, then the subject must be permanently discontinued from all study treatments.
- If DARA is withheld or permanently discontinued, then DURVA, POM, and dex dosing may be continued.
- If POM dosing is withheld or permanently discontinued, then DURVA, DARA, and dex dosing may be continued.
- If dex dosing is withheld or permanently discontinued, then DURVA, DARA, and POM dosing may be continued.

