Appendix E: Durvalumab Treatment Modification and Toxicity Management Guidelines

Note: The toxicity management guidelines in Appendix E-1, E-2, E-3, and E-4 prepared by the sponsor are to assist the investigator in the exercise of his/her clinical judgment in treating these types of toxicities and should be applied to management of adverse events related to study treatment and not ANY adverse event.

Appendix E-1: Durvalumab Treatment Modification and Toxicity Management Guidelines for Immune-mediated Adverse Events

Immune-mediated Reactions

These guidelines are provided as a recommendation to support investigators in the management of potential immune-mediated adverse events (imAEs).

Immune-mediated events can occur in nearly any organ or tissue, therefore, these guidelines may not include all the possible immune-mediated reactions. Investigators are advised to take into consideration the appropriate practice guidelines and other society guidelines (e.g., NCCN, ESMO) in the management of these events. Refer to the section of the table titled "Other -Immune-Mediated Reactions" for general guidance on imAEs not noted in the "Specific Immune-Mediated Reactions" section.

Early identification and management of immune-mediated adverse events (imAEs) are essential to ensure safe use of the study drug. Monitor patients closely for symptoms and signs that may be clinical manifestations of underlying immune-mediated adverse events. Patients with suspected imAEs should be thoroughly evaluated to rule out any alternative etiologies (e.g., disease progression, concomitant medications, infections). In the absence of a clear alternative etiology, all such events should be managed as if they were immune-mediated. Institute medical management promptly, including specialty consultation as appropriate. In general, withhold study drug/study regimen for severe (Grade 3) imAEs. Permanently discontinue study drug/study regimen for life-threatening (Grade 4) imAEs, recurrent severe (Grade 3) imAEs that require systemic immunosuppressive treatment, or an inability to reduce corticosteroid dose to 10 mg or less of prednisone or equivalent per day within 12 weeks of initiating corticosteroids.

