be used for management of Immune Related Hepatitis PLEASE SEE shaded area immediately below this section to find guidance for management of "Hepatitis (elevated LFTS)" in HCC patients	Grade 2	 Hold Study drug/study regimen dose until Grade 2 resolution to Grade ≤1 If toxicity worsens then treat as Grade 3 or Grade 4. If toxicity improves to Grade ≤1 or baseline, resume study drug/study regimen after completion of steroid taper. Permanently discontinue study drug/study regimen for any case meeting Hy's law criteria (AST and/or ALT >3 × ULN + bilirubin >2 × ULN without initial findings of cholestasis (i.e., elevated alkaline P04) and in the absence of any alternative cause.^b 	 For Grade 2: Regular and frequent checking of LFTs (e.g., every 1-2 days) until LFT elevations improve or resolve. If no resolution to Grade ≤1 in 1-2 days, consider discussing with study physician, as needed. If event is persistent (> 2-3 days) or worsens, promptly start prednisone 1-2mg/kg/day PO or IV equivalent. 				

Grade 3 or 4	For Grade 3	For Grade 3 or 4:
Grade 3 of 4	For elevations in transaminases ≤ 8 × ULN, or elevations in bilirubin ≤ 5 × ULN: -Hold study drug/study regimen dose until resolution to Grade ≤1 or baseline Resume study drug/study regimen if elevations downgrade to Grade ≤1 or baseline within 14 days, and after completion of steroid taper Permanently discontinue study drug/study regimen if the elevations do not downgrade to ≤ Grade 1 or baseline For elevations in transaminases > 8 × ULN or elevations in bilirubin > 5 × ULN discontinue study drug/study regimen.	 Promptly initiate empiric IV methylprednisolone at 1 to 2 mg/kg/day or equivalent If still no improvement within 2 to 3 days despite 1 to 2 mg/kg/day methylprednisolone IV or equivalent, promptly start treatment with an immunosuppressant therapy (i.e., mycophenolate mofetil 0.5 – 1 g every 12 hours then taper in consultation with hepatology consult). Discuss with study physician if mycophenolate is not available. Infliximab should NOT be used. Perform Hepatology Consult, abdominal workup, and imaging as appropriate.
	For Grade 4: Permanently discontinue study drug/study regimen.	

	Immune-mediated Reactions			
Hepatitis	Any elevations in	General Guidance	For Any Elevations Described:	
(elevated LFTs) Infliximab should not	AST, ALT, or TB as described below		 Monitor and evaluate liver function test: AST, ALT, ALP, and TB. 	

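### Appendix E-1's Grade 3 hepatitis clauses overlap when both liver tests are raised and only one exceeds its cut-off, and the Grade 3 resume rule does not fit the Hy's law stop printed in the Grade 2 row

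*Combined protocol and SAP*

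**What the plan says.** Section 7.2.4.1 sends sites to Appendix E for durvalumab dose modification. In Appendix E-1, the general hepatitis block is the one that applies to these myeloma subjects, because the shaded block after it is reserved for hepatocellular carcinoma.

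- **Grade 3, hold and resume.** The clause opens "For elevations in transaminases ≤ 8 × ULN, or elevations in bilirubin ≤ 5 × ULN". Treatment is held, then: "Resume study drug/study regimen if elevations downgrade to Grade ≤1 or baseline within 14 days, and after completion of steroid taper". The next sentence requires a permanent stop if the values do not come down, and carries no time limit.
- **Grade 3, stop.** "For elevations in transaminases > 8 × ULN or elevations in bilirubin > 5 × ULN discontinue study drug/study regimen".
- **Grade 2, Hy's law.** "Permanently discontinue study drug/study regimen for any case meeting Hy's law criteria", defined as "AST and/or ALT >3 × ULN + bilirubin >2 × ULN without initial findings of cholestasis" and with no alternative cause. The Grade 3 row neither repeats this nor makes an exception to it.
- **Grade 2, worsening.** "If toxicity worsens then treat as Grade 3 or Grade 4".
- **Consequence of a stop (Section 7.2.4).** "If DURVA is permanently discontinued, then the subject must be permanently discontinued from all study treatments".

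**The concern.** Two sites following the same table could reach opposite decisions for the same liver injury: hold and restart, or discontinue. The two Grade 3 clauses look like complements, but two conditions each joined by *or* are not complements once two analytes are involved. The Hy's law sentence raises a second, independent problem, because it sits in the lower-grade row while the higher-grade row offers resumption at values beyond its thresholds.

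The stake is mainly safety: either re-exposure after a serious liver injury or, through Section 7.2.4, the end of all study treatment. Enrollment is closed, but subjects with clinical benefit may stay on treatment (Section 3.2). The amendment log shows Appendix E-1 was aligned with the durvalumab toxicity guidelines of 17 Nov 2020, so this is current text.

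**Working it through.** No sample size, power or error rate is involved. The check is one of logic on the printed thresholds.

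**Inputs (all from Appendix E-1, Hepatitis).** Let T be AST or ALT and B be bilirubin, each as a multiple of ULN. *Elevation* is read as above ULN.

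- Hold/resume: (1 < T ≤ 8) or (1 < B ≤ 5)
- Stop: (T > 8) or (B > 5)
- Hy's law thresholds: T > 3 and B > 2 (also requires no initial cholestasis and no alternative cause)

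**Step 1: test pairs**

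| T | B | Hold/resume | Stop | Hy's law thresholds |
|---|---|---|---|---|
| 10 | 3 | yes | yes | yes |
| 6 | 6 | yes | yes | yes |
| 10 | 1.3 | yes | yes | no |
| 10 | 1.0 | no | yes | no |
| 6 | 1.0 | yes | no | no |
| 10 | 6 | no | yes | yes |
| 6 | 2.5 | yes | no | yes |
| 6 | 4 | yes | no | yes |
| 8 | 5 | yes | no | yes |

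**Step 2: where the Grade 3 clauses overlap.** The first three rows meet both clauses. The common feature is that both tests are above ULN and exactly one is over its cut-off. There is no overlap when only one test is raised (10, 1.0 and 6, 1.0), when both exceed their cut-offs (10, 6), or when both are raised but neither exceeds its cut-off (the last three rows).

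**Step 3: Hy's law.** The last three rows fall only under hold/resume, yet pass both Hy's law thresholds. With no cholestasis and no alternative cause there are two possible readings:

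- The sentence covers all grades. These Grade 3 cases are then permanent stops under one row and resumable under another.
- The sentence is confined to Grade 2 by its position. A Grade 2 case then stops permanently, while a Grade 3 case with the same pattern may resume.

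The wording of the Hy's law sentence and the link from worsening Grade 2 events to the Grade 3 row favor the first reading, but the text does not settle it.

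**Step 4: are the two problems separate?** As a diagnostic only, replace *or* by *and* in the hold condition (T ≤ 8 and B ≤ 5). The three overlapping pairs then meet only the stop clause. The pairs (6, 2.5), (6, 4) and (8, 5) still meet both hold/resume and the Hy's law thresholds. Repairing the overlap would therefore leave the Hy's law problem in place.

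**Step 5: time limit (secondary).** Resumption needs improvement within 14 days, while the adjacent stop sentence gives no limit. Taken literally, improvement on day 20 meets neither sentence. The parallel stop sentences for Grade 3 colitis and in the hepatocellular-carcinoma block both print 14 days.

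**Comparison within the appendix.** The hepatocellular-carcinoma block limits its rows to isolated AST or ALT rises and adds a separate instruction for combined rises with bilirubin. The general block has no such instruction.

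**The case against.** The strongest reply is that the Grade 3 cell is a tiered list: a lower band is held, a higher band stops, and either analyte over its cut-off is enough for the stop. A careful investigator, with the hepatology consult that the row requires, would probably apply the stricter clause. Appendix E also says that its guidelines "are to assist the investigator in the exercise of his/her clinical judgment", and Section 7.2.4 is the only firm rule quoted here. This softens the problem but does not remove it. No precedence is printed, and clinical judgment cannot tell a site which of two opposite instructions the sponsor intended.

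Several stronger readings are tempting and are not supported:

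- A reader might infer that half of all transaminase/bilirubin combinations, or most Grade 3 hepatitis, is contradictory. Isolated elevations do not overlap, and a count of table cells is not a frequency of patients.
- A reader might infer that a Hy's law case is contradictory and also handled more leniently at the higher grade. These follow from alternative readings of one sentence and cannot both hold.
- A reader might infer that the text permits restart after day 14. It does not, because the resume condition is then unmet. The missing limit may be a dropped phrase, or text lost when the PDF was read.
- A reader might infer a material effect on response or progression results. The documents give neither the number of subjects still on treatment nor a hepatitis rate.

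**Conclusion.** The inconsistency stands on two independent limbs: overlapping Grade 3 clauses when both tests are raised with exactly one over its cut-off, and a Hy's law stop that does not fit the Grade 3 resume rule on either reading. The 14-day mismatch is secondary and needs checking against the source document.

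The conclusion rests on these assumptions. The example values are taken to be Grade 3, because CTCAE grade limits are not printed in the documents. *Elevation* means above ULN. The Hy's law qualifiers are met in the second limb. The stop clause for higher values says discontinue without the word permanently; set against the hold in the same cell, it is read as a stop.

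This is an internal inconsistency in a liver-safety rule, not a flaw in the statistical design. Its importance lies in the safety of subjects still on treatment. It should be corrected even though few subjects may be affected, because the printed text can give opposite instructions for one patient and a permanent durvalumab stop ends all study treatment.

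**What to change.** The sponsor's clinical team must reconcile the passages; this review takes no position on which rule is right. The revised table should:

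- place every transaminase/bilirubin combination within Grade 3 under exactly one clause, or state which clause takes precedence;
- state the grades to which the Hy's law sentence applies, and make the Grade 3 row agree with it;
- use a consistent time limit in the resume and stop sentences, after checking the source document for lost text.

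Because Appendix E-1 follows a separate durvalumab toxicity guideline, the team should check whether the wording originates there, so that the two stay aligned.

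The cost is a wording change in one appendix table, with no new data or visits. Under Section 13.5, a change that is not administrative needs written IRB/EC approval before use, and a substantial one also needs approval from the competent authorities. A letter to sites alone may therefore not suffice.
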